8.3.3. Shipment and Analysis of Samples

Biomarker samples for serum, plasma, RNA, and urine will be stored at -70°C and sent to the central laboratory on dry ice, per instructions in the laboratory manual. Sample labels should include study number, patient randomization number, visit code, collection date and time, and indication that they are biomarker samples. Shipments should be made as specified in laboratory manual. An electronic file containing sample demographics will be e-mailed to the respective biomarker laboratory and the sponsor's biomarker representative for each shipment.

Following DNA extractions of whole blood, the samples will be stored at -70°C and labeled with a new code (ie, double coding), so that genomic data will not be recorded with a patient number. Data will be kept confidential and stored separately.

The biomarker sample analyses will be performed if and when required. Since new techniques continue to be developed, the method and laboratory that will be recommended for the future biomarker analysis cannot be anticipated.

8.4. Methods and Timing of Assessing, Recording, and Analyzing Clinical Pharmacology Data

Methods and timing of assessing clinical pharmacology data are discussed in [Section 3.14](#). Procedures for recording clinical pharmacology data are discussed in [Section 13.1](#), and methods of analyses are discussed in [Section 9.5.4](#).

9. STATISTICS

This is an approximately 19-month, multicenter, randomized, double-blind, parallel-group study to evaluate the long-term safety, tolerability, and efficacy of sc TEV-48125 in adult patients with migraine.

9.1. Sample Size and Power Considerations

There are no statistical considerations for this sample size. A total of 1842 patients (867 patients from Study TV48125-CNS-30049, 675 patients from Study TV48125-30050, and approximately 300 patients who did not participate in the pivotal efficacy studies) are planned for enrollment, and a 30% drop-out rate is anticipated.

9.2. Analysis Sets

9.2.1. Intent-to-Treat Analysis Set

The intent-to-treat (ITT) analysis set will include all patients who are randomized in this study for long-term safety evaluation, regardless if they receive study treatment or not. In this population, treatment will be assigned based on the treatment to which patients are randomized, regardless of which treatment they actually received.

9.2.2. Safety Analysis Set

The safety analysis set will include all patients who receive at least 1 dose of TEV-48125. In this population, treatment will be assigned based upon the treatment patients actually receive, regardless of the treatment to which they are randomized.

9.2.3. Full Analysis Set

The full analysis set (FAS) will include all patients in the safety analysis set and have at least 1 postbaseline efficacy assessment.

9.2.4. Antidrug Antibody Only Analysis Set

The ADA only analysis set will include all patients rolling over from the pivotal efficacy studies for ADA assessment only.

9.3. Data Handling Conventions

Missing diary data will be handled in the same way as in the double-blind pivotal efficacy studies. The details will be provided in the statistical analysis plan.

9.4. Study Population

The ITT analysis set (see Section 9.2.1) will be used for all study population summaries unless otherwise noted. Summaries will be presented overall, by indication, and by treatment group.

9.4.1. Patient Disposition

Data from patients screened, patients screened but not randomized and reason not randomized, patients who are randomized (ie, in the ITT set), patients randomized but not treated, patients in the safety, and FAS analysis sets, patients who complete the study, and patients who withdraw from the study will be summarized using descriptive statistics. Data from patients who withdraw from the study will also be summarized by reason for withdrawal using descriptive statistics.

9.4.2. Demographic and Baseline Characteristics

Patient demographic and baseline characteristics, including medical history, prior medications, and 12-lead ECG findings, will be summarized using descriptive statistics. For continuous variables, descriptive statistics (number [n], mean, standard deviation [SD], median, minimum, and maximum) will be provided. For categorical variables, patient counts and percentages will be provided. Categories for missing data will be presented if necessary.

9.5. Efficacy Analysis

Individuals with CM often complain of continuous levels of very low severity headache, which is typically not modified during the earlier stages of treatment. Accordingly, and following the Classification Committee of the IHS guidelines ([Silberstein et al 2008](#)), headache days of at least moderate severity for both CM and EM patients will be defined for the purpose of this study as a calendar day (0:00 to 23:59) when the patient reports:

- a day with headache pain that lasts ≥ 4 hours with a peak severity of at least moderate severity
- or
- a day when the patient used an acute migraine-specific medication (triptans or ergots) to treat a headache of any severity or duration

Migraine day is endorsed based on the same criteria as described in the pivotal studies. For CM patients, a migraine day is endorsed when at least 1 of the following situations occur:

- a calendar day (0:00 to 23:59) demonstrating ≥ 4 consecutive hours of a headache meeting criteria for migraine with or without aura
- a calendar day (0:00 to 23:59) demonstrating ≥ 4 consecutive hours of a headache meeting criteria for probable migraine, a migraine subtype where only 1 migraine criterion is missing
- a calendar day (0:00 to 23:59) demonstrating a headache of any duration that was treated with migraine-specific medications (triptans and ergot compounds)

For EM patients, a migraine day is endorsed when at least 1 of the following situations occur:

- a calendar day (0:00 to 23:59) demonstrating ≥ 2 consecutive hours of a headache meeting criteria for migraine with or without aura
- a calendar day (0:00 to 23:59) demonstrating ≥ 2 consecutive hours of a headache meeting criteria for probable migraine, a migraine subtype where only 1 migraine criterion is missing

- a calendar day (0:00 to 23:59) demonstrating a headache of any duration that was treated with migraine-specific medications (triptans and ergot compounds)

9.5.1. Primary Endpoint

The primary endpoints for this study are safety-related and are presented in Section 9.7.

9.5.2. Secondary Endpoints

There are no secondary endpoints for this study.

9.5.3. Exploratory Endpoints

Exploratory efficacy endpoints are as follows:

- mean change from baseline (28-day run-in period) in the number of migraine days during the 4-week periods after visits 4, 7, and 13
- mean change from baseline (28-day run-in period) in the number of headache days of at least moderate severity during the 4-week periods after visits 4, 7, and 13
- mean change from baseline (28-day run-in period) in the number of migraine days during the 4-week periods after visits 4, 7, and 13 in patients not receiving concomitant migraine preventive medications at baseline
- mean change from baseline (28-day run-in period) in the number of headache days of at least moderate severity during the 4-week periods after visits 4, 7, and 13 in patients not receiving concomitant migraine preventive medications at baseline
- mean change from baseline (28-day run-in period) in the number of migraine days during the 4-week period after the 1st dose of study drug for new patients and placebo-treated rollover patients
- mean change from baseline (28-day run-in period) in the number of headache days of at least moderate severity during the 4-week period after the 1st dose of study drug for new patients and placebo-treated rollover patients
- mean change from baseline (28-day run-in period) in the number of headache days of any severity during the 4-week periods after visits 4, 7, and 13
- mean change from baseline (28-day run-in period) in the number of days of use of any acute headache medications during the 4-week periods after visits 4, 7, and 13
- proportion of patients reaching at least 50%, 75%, and total (100%) reduction in the number of headache days of at least moderate severity during the 4-week periods after visits 4, 7, and 13
- proportion of patients reaching at least 50% and 75% reduction in the number of headache days of at least moderate severity during the 4-week periods after visit 4 who sustain the same level of response during the 4-week periods after visits 7 and 13
- proportion of patients reaching at least 50%, 75%, and total (100%) reduction in the number of migraine days during the 4-week periods after visits 4, 7, and 13

- proportion of patients reaching at least 50% and 75% reduction in the number of migraine days during the 4-week periods after visit 4 who sustain the same level of response during the 4-week periods after visits 7 and 13
- proportion of patients discontinuing concomitant preventive medications during the treatment period
- mean change from baseline (day 0) in disability score in patients with CM, as measured by the HIT-6, at visits 8 and 14
- mean change from baseline (day 0) in disability score in patients with EM, as measured by the MIDAS questionnaire, at visits 8 and 14
- mean change from baseline (day 0) in quality of life, as measured by the MSQOL questionnaire, at visits 8 and 14
- mean change from baseline (day 0) in patient health status, as measured by the EQ-5D-5L questionnaire, at visits 8 and 14
- assessment of patient satisfaction, as measured by the PGIC scale at visits 3, 5, 8, 11, and 14
- mean change from baseline (day 0) in patient depression status, as measured by the PHQ-2 and PHQ-9, at visits 8 and 14
- mean change from baseline (day 0) in patient work productivity and activity impairment, as measured by the WPAI questionnaire, at visits 8 and 14

9.5.4. Planned Method of Analysis

The FAS (see Section 9.2.3) will be used for all efficacy analyses. Summaries will be presented by indication and treatment group for new patients and rollover patients separately, unless otherwise specified.

9.5.4.1. Primary Efficacy Analysis

Not applicable.

9.5.4.2. Sensitivity Analysis

No sensitivity analyses are planned for this study.

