1.5. Selection of Drugs and Dosages

A detailed description of study drug administration is presented in Section 5.1.

This study is a multi-arm evaluation of the long-term safety, tolerability, and efficacy of the TEV-48125 doses and regimens administered in the pivotal efficacy studies. The doses and regimens for the pivotal efficacy studies are supported by data gathered from animal and human (healthy volunteer) pharmacokinetic studies, in vivo pharmacodynamic neurogenic inflammation experiments in primates, safety and efficacy results of the Phase 2b studies in patients with CM and EM, and population pharmacokinetic and pharmacokinetic/pharmacodynamic models and simulations.

This study will include patients who are rolling over from the pivotal efficacy studies, patients who are not rolling over from the pivotal efficacy studies, and patients who are rolling over from the pivotal efficacy studies for ADA assessment only (ie, these patients will not receive study drug during the current study). Treatments for patients receiving study drug during the current study will be as follows:

- Patients who complete the pivotal efficacy studies and who received active study drug will continue the dose and regimen they received in those studies for 12 months.
- Patients rolling over from the pivotal efficacy studies who received placebo and patients not rolling over will be randomly assigned in a 1:1 ratio to receive monthly TEV-48125 at 225 mg (Note: Patients with CM will receive a 675-mg loading dosing at visit 2 and TEV-48125 at 225 mg at each subsequent visit) or quarterly TEV-48125 at 675 mg.

The doses and regimens selected for the long-term safety study enable a long-term safety evaluation of the doses administered in the pivotal studies as well as examine the maintenance of effect with increased exposure. This study provides the placebo-treated patients from pivotal studies and new patients the opportunity to receive potential benefit from therapeutic doses, and it is the customary way to conduct a long-term safety study by which patients are allowed to continue on their current dose and regimen.

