2.3. Sample Size and Power Considerations

There are no statistical considerations for this sample size. A total of 1842 patients (867 patients from Study TV48125-CNS-30049, 675 patients from Study TV48125-30050, and approximately 300 patients who did not participate in the pivotal efficacy studies) are planned for enrollment, and a 30% drop-out rate is anticipated.

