4.4. Multiple Comparisons and Multiplicity

No inferential analysis will be performed in this study.

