4.5. Handling Withdrawals and Missing Data

A patient's monthly number of days/hours of efficacy variables during the 4-week period after each dose of study drug will be calculated for months 1, 2, 3, 6 and 12. If a patient has missing diary days when calculating the monthly variables, the following method will be used to handle the missing data.

- If a patient has ≥ 10 days of e-diary data for a month, the monthly number of days/hours of efficacy variables will be prorated to 28 days for that month.
- If a patient has < 10 days of e-diary data for a month, the monthly number of days/hours of efficacy variables will be considered as missing for that month.

The missing questionnaire items handling for the MSQOL questionnaire ([Appendix E](#)) is discussed in [Appendix F](#): scoring instruction for MSQOL.

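### Monthly mean changes rest on patients still filling in the diary, so a flat curve from month 3 to month 12 could mask partial waning, and no sensitivity analysis is planned

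*Protocol*

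**What the plan says.** - **Purpose.** Protocol 1.5 says the chosen regimens allow the study to "examine the maintenance of effect with increased exposure".
- **Missing months.** Under SAP 4.5, if a month has at least 10 diary days, "the monthly number of days/hours of efficacy variables will be prorated to 28 days for that month". If it has fewer, "the monthly number of days/hours of efficacy variables will be considered as missing for that month".
- **Means.** SAP 6.4.2.1 summarises change from baseline by month with a 95% confidence interval for eight diary variables, and plots means with standard errors for four of them. It specifies no model and no imputation. This is an observed-case analysis, although the documents do not use the term.
- **Drop-out.** SAP 2.3 states that "a 30% drop-out rate is anticipated", with no time point or definition. Protocol 3.12 names lack of efficacy among its examples of reasons for leaving.
- **Sensitivity.** Protocol 9.5.4.2: "No sensitivity analyses are planned for this study". The SAP adds none for missing data.
- **Responders.** SAP 6.4.1.1 counts early discontinuers as non-responders for the 50%, 75% and 100% reductions. It also defines sustained response from month 3 through months 6 and 12.

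**The concern.** Maintenance will be read from the shape of each regimen's own curve, because the study has no placebo group to show how much of that shape comes from attrition. The patients behind the month-12 point are those who still supply diary data, and they need not resemble those behind the month-3 point. If poorer responders leave more often, the later means improve or hold steady without any patient doing better. The means and the responder rates for the same month also treat leavers differently: the means omit them and the rates count them as failures. The two summaries could diverge, and nothing planned would explain why. At stake is whether a level curve can be reported as maintained effect.

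**Working it through.** **The plan's own figure.** Protocol 9.1 gives "A total of 1842 patients (867 patients from Study TV48125-CNS-30049, 675 patients from Study TV48125-30050, and approximately 300 patients who did not participate". The sum 867 + 675 + 300 = 1842 reproduces. Thirty percent drop-out means 1842 × 0.30 ≈ 553 lost and 1842 × 0.70 ≈ 1289 remaining. If the new patients split 150/150, that leaves about 712 of 1017 with chronic migraine and 578 of 825 with episodic migraine. There is no power calculation to check: "There are no statistical considerations for this sample size".

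**Size of the shift.** Let d be the share without month-12 data, C the completers' mean change, and G the number of days by which the others improve less. The mean for everyone is (1 − d)C + d(C + G) = C + dG, so the observed mean is too favourable by dG. Take d = 0.30 and, as assumptions, C = −5.0 and G = 2 to 4:

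- G = 2: 0.7 × (−5.0) + 0.3 × (−3.0) = −4.4, a shift of 0.6 day.
- G = 4: 0.7 × (−5.0) + 0.3 × (−1.0) = −3.8, a shift of 1.2 days.

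**Ceiling.** If change is normally distributed and exactly the worst 30% leave, the observed mean moves by φ(z₀.₃₀)/0.70 = 0.497 SD. For assumed SDs of 4, 5 and 6 days this is 2.0, 2.5 and 3.0 days.

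**Simulation.** One million patients were simulated with month-3 mean −4 to −5 days, SD 4 to 6, month-3 to month-12 correlation 0.5 to 0.9, and 30% drop-out depending on month-3 response. All of these values are assumed.

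| Selection | Apparent gain at month 12 with no true change | Share of month-3 effect that a flat curve could hide |
|---|---|---|
| Mild | 0.3–0.8 day | 7–16% |
| Moderate | 0.5–1.4 days | 12–28% |
| Worst 30% all leave | 1.0–2.7 days | 25–56% |

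**What the responder rate would show.** Take mean −4, SD 5, correlation 0.7 and moderate selection. A flat mean curve then hides a loss of 0.88 day (0.88/4 = 22%). The 50% responder rate under the planned rule falls from 0.46 at month 3 to 0.32 at month 12, while the true month-12 rate is 0.39. With the same settings but no selection and no waning, the planned rate is 0.46 × 0.70 = 0.32 and the true rate stays at 0.46. The planned rate falls equally in both cases, so it signals that patients left but does not show whether the effect waned.

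**The case against.** The strongest reply is that the plan already contains a maintenance analysis. The sustained-responder endpoint follows individual patients from month 3 to months 6 and 12, and counting discontinuers as non-responders pushes responder rates down rather than up. A reader who saw a level mean beside a falling responder rate would be warned. This stands as a partial check. It covers two variables only, and leaves untouched the plotted means, headache days of any severity, acute-medication days and the questionnaire scores. SAP 6.4.1.1 also does not say how a continuing patient with fewer than 10 diary days in a month is counted.

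Second, Protocol 3.14.4.1 asks patients who stop treatment to keep attending and to complete efficacy evaluations, so stopping the drug need not mean a missing diary. The 30% is not tied to month 12, and lack of efficacy is only one of the listed examples of reasons to leave. Patients who leave before month 3 would shrink the month-3 to month-12 artefact. All of this stands, and it is why the size above is conditional.

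Third, efficacy is exploratory throughout, "No inferential analysis will be performed in this study", and maintenance appears in the dose rationale rather than among the objectives. The number of patients accompanies every summary, and withdrawals are tabulated by reason. This limits the weight of the point. Counts show how many left, but not how they were responding.

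**Conclusion.** The point holds in a limited form. The mean curves alone cannot separate maintained effect from a changing set of patients, and a flat or improving curve could mask partial waning. The size is 0.6 to 1.2 days if 30% of patients lack month-12 data, they improve by 2 to 4 days less than completers, and they were still counted at month 3. None of these three conditions is established by the documents.

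A reader might go further and infer that attrition alone could account for the month-12 effect. The documents do not support that. In the worked example −3.8 to −4.4 of the −5.0 days remains, that is 76% to 88%. At 30% drop-out the distortion cannot exceed about 0.5 SD under normality. Erasing a 5-day effect would need G = 5/0.30 = 16.7 days. That leavers respond worse is plausible but is not stated anywhere. The change is worth making to the reporting of exploratory means and does not bear on the safety objective.

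**What to change.** In Protocol 9.5.4.2 and SAP 6.4.2.1, add the following beside the planned means, by indication and regimen, descriptively and without tests:

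- (a) Month-3 and month-6 means in patients who have month-12 data, so that the curve follows the same people, together with month-3 means by later drop-out status. Note that the completer set is itself selected.
- (b) Mixed-model repeated-measures estimates using all observed months, with the missing-at-random assumption stated.

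Both use data already collected and change nothing in study conduct. The cost is a little more analysis and possibly a less favourable month-12 figure. Neither addition makes the month-12 mean attributable to drug in a study without a control group.

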9.5.4.3. Secondary Efficacy Analysis

Not applicable.

9.5.4.4. Exploratory Efficacy Analysis

All efficacy variables will be summarized descriptively. For continuous variables, descriptive statistics (n, mean, SD, standard error of mean, median, minimum, and maximum) will be provided for actual values and changes from baseline to each visit. For categorical variables, frequency and percentage will be provided. For rollover patients, their baseline is defined as the baseline in the pivotal efficacy studies.

9.6. Multiple Comparisons and Multiplicity

No inferential analysis will be performed in this study.

9.7. Safety and Tolerability Endpoints and Analysis

Safety and tolerability analyses will be performed on the safety analysis set. Summaries will be presented overall, by indication and by treatment group.

9.7.1. Safety and Tolerability Endpoints

The safety and tolerability endpoints for this study are as follows:

- occurrence of adverse events throughout the study
- changes from baseline in clinical laboratory (serum chemistry, hematology, coagulation, and urinalysis) test results
- abnormal standard 12-lead ECG findings
- changes from baseline in vital signs (pulse, systolic and diastolic blood pressure, body temperature, and respiratory rate) measurements
- abnormal physical examination findings
- abnormal local injection site tolerability findings (ie, erythema, induration, and ecchymosis) and occurrence of injection site pain
- suicidal ideation and behavior as suggested by the eC-SSRS

Safety and tolerability measures and time points are provided in [Table 1](#) (patients rolling over from the pivotal efficacy studies), [Table 2](#) (patients not rolling over from the pivotal efficacy studies), and [Table 3](#) (patients rolling over from the pivotal efficacy studies for ADA assessment only).

9.7.2. Safety and Tolerability Analysis

All adverse events will be coded using the Medical Dictionary for Regulatory Activities. Each patient will be counted only once in each preferred term or system organ class category for the analyses of safety. Summaries will be presented for all adverse events (overall and by severity), adverse events determined by the investigator to be related to study treatment (ie, reasonable possibility; see [Section 7.1.4](#)) (defined as related or with missing relationship) (overall and by severity), serious adverse events, and adverse events causing withdrawal from the study. Patient listings of serious adverse events and adverse events leading to withdrawal will be presented.

Injection site erythema, induration, ecchymosis, and pain will be assessed, and severity will be graded as described in [Section 7.9](#), and findings will be listed and summarized.

Changes in laboratory and vital signs measurement data will be summarized descriptively. All values will be compared with prespecified boundaries to identify potentially clinically significant changes or values, and such values will be listed.

The use of concomitant medications will be summarized by therapeutic class using descriptive statistics. Concomitant medications will include all medications taken while the patient is treated with study drug.

Safety data will be summarized descriptively overall, by diagnosis, and by treatment group. For continuous variables, descriptive statistics (n, mean, SD, median, minimum, and maximum) will be provided for actual values and changes from baseline to each time point. For categorical variables, patient counts and percentages will be provided. Descriptive summaries of serious adverse events, patient withdrawals due to adverse events, and potentially clinically significant abnormal values (clinical laboratory or vital signs) based on predefined criteria will also be provided.

If any patient dies during the study, a listing of deaths will be provided and all relevant information will be discussed in the patient narrative included in the clinical study report.

